8. SOFTWARE

All analyses will be done using SAS Version 9.4 or higher.

10. APPENDIX

10.1. Summary of Statistical Analyses

Primary Efficacy Analysis – Part B:

Endpoint	Analysis Populations	Estimand	Statistical Method	Supportive Analysis	Subgroup Analysis	Other Analyses
Primary Endpoint						
Percent change from baseline in calculated LDL-C at Week 24	ITT	ITT estimand: The calculated LDL-C at week 24 will be the LDL-C value obtained within the week 24 efficacy analysis window, regardless of adherence to treatment and subsequent therapies.	PMM	Yes	Yes	1. MMRM - ITT 2. MMRM - mITT

10.2. Windows for Analysis Time Points

Below are the definitions for the visit windows programmatically imposed on measures repeatedly collected over the course of the study. These visit windows reflect the study schedule of assessments as described in the protocol.

The visit windows are constructed using ranges applied to the number of days in study (study days) when the measure is collected. Below are the relevant definitions for the analysis visit windows:

1. Study day is defined as the number of days since the first study treatment administration +1. The first study treatment occurs on Study Day 1.
2. Part C study day is defined as the number of days since the first Part C study treatment administration+1
3. Since the protocol specifies that measurements be collected before study treatment is administered on a given day, it is appropriate that baseline include Day 1.

Table 1: Global Analysis Windows for Part A

Visit label	Targeted Study Day	Analysis Window in Study Day
Baseline	1	Measurement obtained closest to first study treatment, while remaining prior to first study treatment
Week 1	8	2 to 11
Week 2	15	12 to 18
Week 3	22	19 to 25
Week 4	29	26 to 35
Week 6	43	36 to 49
Week 8	57	50 to 63
Week 10	71	64 to 77
Week 12	85	78 to 98
Week 16	113	99 to 140
FU- W8	For patients prematurely discontinued Part A: EOT visit study day + 56 days For patients completed Week 16 visit: 169	For patients prematurely discontinued Part A: EOT visit to 84 days after EOT visit For patients completed Week 16 visit: 141 to 196
Study days are calculated from the day of first IMP infusion, the day of first IMP infusion being Day 1.		

Table 2: Global Analysis Windows for Part B

Visit label	Targeted Study Day	Analysis Window in Study Day
Baseline	1	Measurement obtained closest to first study treatment, while remaining prior to first study treatment
Week 1	8	2 to 11
Week 2	15	12 to 21
Week 4	29	22 to 35
Week 6	43	36 to 49
Week 8	57	50 to 70
Week 12	85	71 to 98
Week 16	113	99 to 126
Week 20	141	127 to 154
Week 24	169	155 to 196
FU- W8	For patients prematurely discontinued trt: last study trt + 84 days For patients completed Part B trt period: 225	For patients prematurely discontinued trt: 56 to 97 days after last trt For patients completed Part B trt period: 197 to 238
FU-W12	For patients prematurely discontinued trt: last study trt + 112 days For patients completed Part B trt period: 253	For patients prematurely discontinued trt: 98 to 125 days after last trt For patients completed Part B trt period: 239 to 266
FU-W16	For patients prematurely discontinued trt: last study trt + 140 days For patients completed Part B trt period: 281	For patients prematurely discontinued trt: 126 to 153 days after last trt For patients completed Part B trt period: 267 to 294
FU-W20	For patients prematurely discontinued trt: last study trt + 168 days For patients completed Part B trt period: 309	For patients prematurely discontinued trt: 154 to 181 days after last trt For patients completed Part B trt period: 295 to 322
Study days are calculated from the day of first IMP infusion, the day of first IMP infusion being Day 1.		

Table 3: Efficacy Analysis Windows for Part B

Visit Label	Targeted study day	Analysis window in study days
Baseline	1	Measurement obtained closest to first study treatment, while remaining prior to first study treatment
Week 1	8	2 to 11
Week 2	15	12 to 21
Week 4	29	22 to 42
Week 8	57	43 to 70
Week 12	85	71 to 98
Week 16	113	99 to 126
Week 20	141	127 to 154
Week 24	169	155 to 196

Table 4: Global Analysis Windows for Part C

Visit label	Targeted Study Day	Analysis Window in Study Day
Week 0	1	1
Week 4	29	15 to 42
Week 8	57	43 to 70
Week 12	85	71 to 98
Week 16	113	99 to 126
Week 20	141	127 to 154
Week 24	169	155 to 182
Week 28	197	183 to 210
Week 32	225	211 to 238
Week 36	253	239 to 266
Week 40	281	267 to 294
Week 44	309	295 to 322
Week 48	337	323 to 364
FU – W8	For patients prematurely discontinued trt: last study trt + 56 days For patients completed Part C trt period: 365	For patients prematurely discontinued trt: 28 to 69 days after last trt For patients completed Part C trt period: 337 to 378
FU – W12	For patients prematurely discontinued trt: last study trt + 84 days For patients completed Part C trt period: 393	For patients prematurely discontinued trt: 70 to 97 days after last trt For patients completed Part C trt period: 379 to 406

Visit label	Targeted Study Day	Analysis Window in Study Day
FU – W16	For patients prematurely discontinued trt: last study trt + 112 days For patients completed Part C trt period: 421	For patients prematurely discontinued trt: 98 to 139 days after last trt For patients completed Part C trt period: 407 to 448
FU – W24	For patients prematurely discontinued trt: last study trt + 168 days For patients completed Part C trt period: 477	For patients prematurely discontinued trt: 140 to 195 days after last trt For patients completed Part C trt period: 449 to 504

Study days are calculated from the day of first Part C IMP infusion, the day of first Part C IMP infusion being Day 1.

Table 5: Pooled Analysis Windows for the Integrated Data Pool

Patients	Part A Patients	Part B Patients	
Visit Label	Targeted Study Day from Part C Day 1	Targeted Study Day from Part B Day 1	Analysis Window in Study Day in Combine Open-Label Treatment Period
Baseline	N/A	1	Part A patients: measurement obtained closest to first Part A study treatment, while remaining prior to first Part A study treatment. Part B patients: measurement obtained closest to first Part B study treatment, while remaining prior to first Part B study treatment.
Week 4	29	29	15 to 42
Week 8	57	57	43 to 70
Week 12	85	85	71 to 98
Week 16	113	113	99 to 126
Week 20	141	141	127 to 154
Week 24	169	169	155 to 182
Week 28	197	197	183 to 210
Week 32	225	225	211 to 238
Week 36	253	253	239 to 266
Week 40	281	281	267 to 294
Week 44	309	309	295 to 322
Week 48	337	337	323 to 350
Week 52	N/A	365	351 to 378
Week 56	N/A	393	379 to 406

Patients	Part A Patients	Part B Patients	
Visit Label	Targeted Study Day from Part C Day 1	Targeted Study Day from Part B Day 1	Analysis Window in Study Day in Combine Open-Label Treatment Period
Week 60	N/A	421	407 to 434
Week 64	N/A	449	435 to 462
Week 68	N/A	477	463 to 490
Week 72	N/A	505	491 to 518
FU – W12	Last study trt + 84 days	Last study trt + 84 days	70 to 97 days after last trt
FU – W16	Last study trt + 112 days	Last study trt + 112 days	98 to 139 days after last trt
FU – W24	Last study trt + 168 days	Last study trt + 168 days	140 to 195 days after last study trt

Study days for Part A patients are calculated from the day of first Part C IMP infusion, the day of first Part C IMP infusion being Day 1.
 
Study days for Part B patients are calculated from the day of first Part B IMP infusion, the day of first Part B IMP infusion being Day 1.
			

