14. At weeks 8 and 16 of the follow-up period all patients will be contacted by phone to query LMT compliance, to inquire about AEs or changes to concomitant medications, confirm required contraception use, and remind patients of pregnancy reporting. Sexually active females of childbearing potential will report the results of their home pregnancy test. For patients who decide to enter a compassionate use or early access program, the EOT visit will be their last visit and they will forgo the 24-week follow-up period.
15. Overlapping assessments completed at the EOT visit of Part A or Part B do not need to be duplicated during visit 1 of Part C. Part C visit 1 should occur on the same day as Part A visit 11 or Part B visit 11. All necessary assessments are listed in the applicable SOE (Part A or Part B) column for visit 11.
16. Patient can only receive the dose once all assessments from Part A or Part B Visit 11 are completed.
17. For patients who decide to enter a CUP or EAP, the EOT visit will be their last visit and they will forgo the 24-week follow-up period.

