- The total number of patients who completed Part B treatment period as collected on the End of Treatment e-CRF.

- The total number of patients who completed Part B treatment period, defined as at least 20 weeks of study treatment administration and visit week 24 performed.
- The total number of patients who prematurely discontinued Part B treatment, and the reasons for discontinuation collected on the End of Treatment e-CRF
- The total number of patients in Part B who do not proceed into Part C and complete the last study follow-up visit (i.e. Follow-up Week 20).
- The total number of patients in Part B who do not proceed into Part C and do not complete the study follow-up period, defined as the last visit performed less than 22 weeks after the last study treatment administration. Patients who died during the study are excluded.

Patient milestone categories for Part C are defined below. As applicable, percentages will be calculated using a denominator of the number of patients receiving Part C study treatment.

- The total number of patients receiving Part C study treatment.
- The total number of patients ongoing in Part C (applicable for the first step and second step analyses)
- The total number of patients who completed Part C treatment period as collected on the End of Treatment e-CRF.
- The total number of patients who completed Part C treatment period, defined as at least 44 weeks of Part C study treatment administration and Part C visit week 48 performed.
- The total number of patients who prematurely discontinued study treatment during Part C, and the reasons for discontinuation collected on the End of Treatment e-CRF.
- The total number of patients in Part C who complete the last study follow-up visit (i.e. Follow-up week 24).
- The total number of patients who did not complete the study follow-up period, defined as the last visit performed less than 22 weeks after the last study treatment administration. Patients who died during the study are excluded.

The following patient populations for analyses are defined in Section 4.2:

- Efficacy populations (for Part B only): ITT and mITT populations
- Safety analysis set
- Part C safety analysis set
- Pooled safety analysis set
- Anti-evincumab antibody (ADA) analysis set
- Neutralizing anti-evincumab antibody (NAb) analysis set
- Pharmacokinetic (PK) analysis set
- Target analysis set

- Concentration-Response (C-R) analysis set

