4.6. Study Treatment Exposure and Compliance Variables

Study treatment exposure variables for infusions administered in Part A are listed below with associated definitions:

- The total number of Part A study treatment infusions by patient.
- Patient duration of Part A observation treatment period in weeks defined as: (last visit date during the Part A observation period - first study treatment administration date in Part A)/7.

Study treatment exposure variables for infusions administered in Part B are listed below with associated definitions:

- Patient duration of Part B study treatment exposure in weeks defined as: (last Part B study treatment administration date +28 – first Part B study treatment administration date)/7. Unplanned intermittent discontinuations in study treatment will be addressed on a case-by-case basis, since this is expected to be a rare occurrence. Values will be rounded to one decimal place.
- The total number of Part B study treatment infusions by patient.
- The following categories will be used for treatment exposure at 4 week intervals: ≥ 1 day and < 4 weeks, ≥ 4 weeks and < 8 weeks, ≥ 8 weeks and < 12 weeks, ≥ 12 weeks and < 16 weeks, ≥ 16 weeks and < 20 weeks, ≥ 20 weeks and < 24 weeks, ≥ 24 weeks.

Study treatment exposure variables for infusions administered in Part C are listed below with associated definitions:

- Patient duration of Part C study treatment exposure in weeks defined as: (last Part C study treatment administration date +28 – first Part C study treatment administration date)/7. Unplanned intermittent discontinuations in study treatment will be addressed on a case-by-case basis, since this is expected to be a rare occurrence. Values will be rounded to one decimal place.
- The total number of Part C study treatment infusions by patient.
- The following categories will be used for treatment exposure at 4 week intervals: ≥ 1 day and < 4 weeks, ≥ 4 weeks and < 8 weeks, ≥ 8 weeks and < 12 weeks, ≥ 12 weeks and < 16 weeks, ≥ 16 weeks and < 20 weeks, ≥ 20 weeks and < 24 weeks, ≥ 24 weeks and < 28 weeks, ≥ 28 weeks and < 32 weeks, ≥ 32 weeks and < 36 weeks, ≥ 36 weeks and < 40 weeks, ≥ 40 weeks and < 44 weeks, ≥ 44 weeks and < 48 weeks, ≥ 48 weeks

Study treatment exposure variables on the integrated data pool (Section 2.4) are listed below with associated definitions:

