- Cumulative patient duration of study treatment exposure in weeks defined as: Part C treatment exposure for Part A patients, and Part B treatment exposure plus Part C treatment exposure for Part B patients.
- Cumulative total number of study treatment infusions by patient defined as: total number of Part C infusions for Part A patients, and total number of Part B infusions plus total number of Part C infusions for Part B patients.
- The following categories will be used for cumulative patient treatment exposure at 4 week intervals: ≥ 1 day and < 4 weeks, ≥ 4 weeks and < 8 weeks, ≥ 8 weeks and < 12 weeks, ≥ 12 weeks and < 16 weeks, ≥ 16 weeks and < 20 weeks, ≥ 20 weeks and < 24 weeks, ≥ 24 weeks and < 28 weeks, ≥ 28 weeks and < 32 weeks, ≥ 32 weeks and < 36 weeks, ≥ 36 weeks and < 40 weeks, ≥ 40 weeks and < 44 weeks, ≥ 44 weeks and < 48 weeks, ≥ 48 weeks and < 52 weeks, ≥ 52 weeks and < 56 weeks, ≥ 56 weeks and < 60 weeks, ≥ 60 weeks and < 64 weeks, ≥ 64 weeks and < 68 weeks, ≥ 68 weeks and < 72 weeks, ≥ 72 weeks, etc.

With respect to patient treatment administration compliance, the study treatment is administered during the investigative site visits and therefore study compliance will be assessed by infusion frequency for Part B treatment period, and Part C treatment period, specifically:

- The mean infusion/injection frequency for study treatment will be defined for each patient as the average number of days between 2 consecutive infusions: (last study treatment administration date – first study treatment administration date) / (number of infusions - 1), for patients receiving at least 2 infusions.

All important and minor protocol deviations potentially impacting efficacy analyses, drug-dispensing irregularities, as well as other deviations, will be collected and reviewed on an ongoing basis throughout the study as described in the Protocol Deviation Plan (PDP). Both monitoring collected and programmatically derived deviations are listed and defined in the PDP.

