6.4. Visit Windows

Visit windows will be programmatically imposed on those efficacy and safety measures repeatedly collected over the course of the study. These visit windows are derived from the number of days in study, specifically assigning day ranges to represent the study assessment schedule provided in the protocol. Data analyzed by time point (including efficacy, laboratory safety data, vital signs, and ECG) will be summarized using the analysis windows given in [Appendix 10.2](#) (i.e. efficacy analysis windows for Part B efficacy and global analysis windows for others). These analysis windows will be applicable for all analyses, and they are defined to provide more homogeneous data for time point-specific analyses. If multiple valid values of a variable exist within an analysis window, the nearest from the targeted study day will be selected for analysis, unless otherwise specified. If the difference is a tie, the value after the targeted study day will be used. If multiple valid values of a variable exist within a same day, then the first value of the day will be selected when time is available, else the scheduled visit will be selected.

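### SAP Table 4 places days 337 to 364 in both Week 48 and FU-W8 for Part C completers, so an on-time end-of-treatment sample has two labels; the last Part C dosing visit also needs confirming

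*SAP*

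**What the plan says.** **Windows.** SAP Appendix 10.2, Table 4 gives Week 48 as days 323 to 364, target day 337. For completers, FU-W8 has target day 365 and the window "For patients completed Part C trt period: 337 to 378". The last completer row, FU-W24, has target day 477 and the window "For patients completed Part C trt period: 449 to 504". For patients who stop early, the same table counts follow-up from the last dose: 28–69, 70–97, 98–139 and 140–195 days. Table 5, for the pooled data, counts follow-up from the last dose for everyone, ending with "140 to 195 days after last study trt". It has no FU-W8 row and ends Week 48 at day 350.

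**Selection rule.** SAP 6.4 says: "If multiple valid values of a variable exist within an analysis window, the nearest from the targeted study day will be selected for analysis". It adds rules for ties and for several values on one day. It does not mention a value that lies in two windows.

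**Nature of FU-W8.** Protocol 9.1.1.3, footnote 14: "At weeks 8 and 16 of the follow-up period all patients will be contacted by phone to query LMT compliance". The schedule lists no lipid, central-laboratory, vital-sign, ECG or PK sample at that contact.

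**Last Part C dose.** Protocol Table 3 and the Part C schedule in SAP 10.7 both mark study drug at all 13 treatment visits, V1 to V13. V13 is the EOT visit at week 48, with a window of ±5 days. SAP 2.1 and 2.3 describe 48 weeks of treatment followed by 20 weeks of follow-up. SAP 4.5 has treatment completion "defined as at least 44 weeks of Part C study treatment administration and Part C visit week 48 performed".

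**The concern.** Analysis windows should give each value one label. Here the target day of the EOT visit carries two, and the written rule gives no way to choose between them. Two programmers following the SAP could put the same sample under Week 48, under FU-W8, or under both. Week 48 is the last on-treatment point in Part C. For Tanner stage, sex hormones and carotid ultrasound it is one of only two scheduled on-treatment points in Part C, the other being week 24.

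The completer follow-up rows raise a second question. They look as if they were built on a week-44 last dose, which does not match the dose mark at week 48 in either schedule.

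**Working it through.** **Inputs.** Part C day 1 is the first Part C dose (SAP 10.2), so week w falls on day 7w + 1. Week 44 is day 309 and week 48 is day 337. The windows and schedule marks are those given above. The Part C treatment period for by-visit summaries ends at last dose + 28 days (SAP 5.8.3).

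**1. Where Table 4's completer rows come from.** Day 309 plus the early-stopper offsets:

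| Row | Offset (days) | Day 309 + offset | Table 4, completers | Day 337 + offset |
|---|---|---|---|---|
| FU-W8 | 28–69 | 337–378 | 337–378 | 365–406 |
| FU-W12 | 70–97 | 379–406 | 379–406 | 407–434 |
| FU-W16 | 98–139 | 407–448 | 407–448 | 435–476 |
| FU-W24 | 140–195 | 449–504 | 449–504 | 477–532 |

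Table 4 is reproduced exactly by a last dose on day 309. Nothing is miscalculated; the rows rest on a week-44 last dose.

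**2. The overlap.** Days 323–364 and 337–378 share 337–364, which is 364 − 337 + 1 = 28 days. The permitted EOT days are 337 ± 5 = 332–342, 11 days. Of these, 337–342 (6 of 11) lie in both windows. This holds whichever visit carries the last dose.

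Elsewhere the rows abut. Table 4's later completer rows meet at 378/379, 406/407 and 448/449. In Part B (Table 2), Week 24 ends at day 196 and completer FU-W8 starts at day 197.

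**3. Does a doubly labelled sample reach a planned table?** The Part C by-visit summaries (lipids 5.7.4, laboratory 5.8.3, vital signs 5.8.4, ECG 5.8.5, Tanner stage 5.8.6, other variables 5.9) are limited to the treatment period.

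- Last dose at the week-48 EOT visit: the period ends 28 days later, so all 6 days are inside.
- Last dose at week 44, on day 309: the period ends on day 309 + 28 = 337, so 1 of the 6 days is inside.
- Week-44 dose on day 304: the period ends on day 332, so 0 of 6. On day 314: it ends on day 342, so 6 of 6. A day-337 sample is inside only if that dose was on or after day 309.

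**4. Which last dose do the documents support?**

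- *Week 44.* The 20-week follow-up fits: 48 + 20 = week 68 = day 477, the FU-W24 target. So does the 44-week element in SAP 4.5. Exposure by SAP 4.6 is (309 + 28 − 1)/7 = 48.0 weeks, or 24.0 + 48.0 = 72.0 weeks with Part B. These match the top categories in "≥ 44 weeks and < 48 weeks, ≥ 48 weeks" and "≥ 68 weeks and < 72 weeks, ≥ 72 weeks, etc". With a day-337 last dose they would be 52.0 and 76.0 weeks.
- *Week 48.* Both schedules mark a dose at V13. The protocol's maximum durations are 8 + 2 + 16 + 48 + 24 = 98 and 8 + 2 + 24 + 48 + 24 = 106 weeks. With 20 weeks after week 48 they would be 94 and 102. As upper limits, 98 and 106 fit week 48 better but do not require it.

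**5. Follow-up labels if week 48 is the last dose.** For a day-337 dose, the +12-week visit is 421 ± 5 = 416–426, all labelled FU-W16. The end-of-study visit is 505 ± 5 = 500–510, and 505–510 (6 of 11 days) have no window. That last count depends on the dose day: 1 of 11 for a day-332 dose (495–505) and 11 of 11 for a day-342 dose (505–515). If week 44 is the last dose, Tables 4 and 5 agree on FU-W12, FU-W16 and FU-W24.

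**The case against.** The strongest reply is that no sensible programmer would go wrong. Day 337 is the Week 48 target and lies 28 days from the FU-W8 target. Even day 342 is 5 days from the one and 23 from the other. FU-W8 has no scheduled sample to compete, and patients who go to compassionate use or early access have no follow-up at all. This stands as a statement about the likely outcome. It does not supply the missing rule: SAP 6.4 chooses between values within a window, not between windows for one value.

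A reader might infer more than the documents support, in three ways:

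- **That the completer follow-up rows are wrong.** They are wrong only if week 48 is the last dose. SAP 2.1, 2.3, 4.5 and 4.6 fit week 44, and on that reading the V13 dose mark is the error.
- **That shifted follow-up labels distort reported results.** The Part C by-visit summaries stop at the end of the treatment period, so no affected table has been identified.
- **That every on-time EOT sample enters the tables with two labels.** On the week-44 reading, a dose on days 304–308 ends the treatment period on days 332–336, and a day-337 sample is then excluded.

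Nor can the conflict over the last dose be put down to the SAP being written against Amendment 1. The SAP's own schedule marks the week-48 dose.

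**Conclusion.** The overlap is an error in a stated rule, and it does not depend on which visit carries the last dose. It covers 28 days and 6 of the 11 permitted EOT days, including the target day. The affected values belong in Week 48.

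The consequence is small. It is limited to descriptive Part C by-visit tables. It arises if the last dose is at week 48 or, for a day-337 sample, if a week-44 last dose fell on or after day 309. Part B endpoints use Table 3 and are unaffected, as are TEAE and PCSV counts, which use the TEAE period. The pooled summaries use Table 5.

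The conflict over the last Part C dose is real but undecided. It is a question for the sponsor, with no shown effect on a planned table. How many patients skip follow-up for compassionate use or early access is not stated. Severity: minor.

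**What to change.** Confirm the last Part C dosing visit, then correct Table 4 before programming.

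- **If week 44:** end Week 48 at day 350, as Table 5 does, and start FU-W8 at day 351. Keep the other follow-up windows. Remove the V13 dose mark from protocol Table 3 and SAP 10.7. Restating the maximum durations as 94 and 102 weeks is optional.
- **If week 48:** define the completer follow-up windows from each patient's actual last dose (28–69, 70–97, 98–139 and 140–195 days after). End Week 48 on the day before that patient's FU-W8 window starts, with no fixed cap at day 364. For last doses on days 332, 337 and 342, Week 48 then ends on days 359, 364 and 369. A fixed cap would leave days 365–369 without a window in the last case. Align SAP 2.1, 2.3 and 4.5 with the schedules.

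The cost is an edit to SAP tables and text plus window programming. The week-44 option also needs a correction to the protocol schedule.
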